1. Number of subjects: 20 subjects will be recruited at each of three study sites, leading to a total of 60 subjects. The subjects will be divided randomly into two training cohorts, with 30 subjects receiving one form of visual discrimination training therapy, while the other 30 will receive another form of visual discrimination training.

2. Gender and age range: Subject gender is intended to have an even distribution. Women and men are both susceptible to the conditions that would qualify participation as study subjects in the proposed research. All subjects who have sustained vision losses as a result of brain damage, that are able to give informed consent and are willing and able to undergo testing and training will be eligible for inclusion in this study, subject to the limitations described in the following paragraph. Since vision losses as a result of brain damage do occur in women, we will aim to recruit equal numbers of men and women in the proposed study.

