6. At least two reliable HVF's demonstrating good fixation and a stable homonymous incomplete (e.g., quadrantanopia or relative defect) or complete hemianopia
7. Reliable HVFs with repeat HVFs if randomization takes place more than 4 weeks after screening visit
8. A homonymous, contiguous visual deficit measured by the 24-2 HVF to be a minimum of two testing locations high and two testing locations wide, where impaired locations are any that measure a threshold of less than 15 dB
9. Demonstration of good fixation on visual training task – able to fixate the small targets presented as fixation letters reliably for 1000ms with jitter over less than 1 degree of visual angle in any direction away from target edge

Exclusion Criteria at Screening Visit

1. Physical, neurological or mental disability that would interfere with study intervention
2. Concurrent participation in "vision therapy" other than standard occupational or physical therapy
3. Unreliable visual fields on prior testing, indicated by greater than 20% fixation losses, false positives, or false negatives.
4. Inability to discontinue medications judged to affect training and/or assessment (e.g., Ritalin, amphetamines, dopamines, or chemotherapeutic agents)

5. Physical condition likely to preclude completion of the clinical trial (e.g. end-stage or uncontrolled cancer, uncontrolled epilepsy, or end-stage heart disease)
6. Ocular or neurological condition that would interfere with training or assessment (e.g. damage to the optic nerves or lateral geniculate nucleus, any degenerative ocular condition)
7. Best corrected vision worse than 20/40 in either eye
8. Impaired foveal Humphrey sensitivity as indicated by the HVF tests.
9. Presence of vision loss resulting from ocular disease or disorder
10. Presence of bilateral visual acuity loss from any source

Additional Exclusion Criteria at Randomization Visit

1. Inability to demonstrate fixation stability on eye movement monitored testing
2. Inability to follow training instructions

Concomitant Medications

1. No medication is required for participation in the study
2. Allowed Concomitant Medications: Any medications that do not affect learning or motor performance are allowed. All concomitant medications must be used according to the prescriber's instructions.

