Eye examination: A complete medical history, eye history, and eye examination will be performed in order to determine eligibility for the study. A comprehensive, routine dilated eye exam that includes slit lamp examination and retinal optical coherence tomography (OCT), will be performed on each patient by a qualified ophthalmologist or neuro-ophthalmologist at each site to verify ocular health. OCT should have a signal strength of at least 6, otherwise the test should be repeated. If any problems or signs of ongoing, developing or progressing eye disease are observed, this will constitute grounds for exclusion from the study. The eye examination will include Snellen best corrected acuity, intraocular pressure measurement, exophthalmometry, motility, external examination, slit lamp examination, dilated fundus examination and OCT imaging of the retina.

Visual field testing: Certified technicians will perform 24-2 Humphrey visual fields on each subject. Fixation and pupil monitoring will be “on” for each test. The examination will be performed twice with a 30-minute rest period after each test. Examinations need to be done twice at baseline, with the second test used for future analysis, to ensure that patients are proficient in performing the tests at baseline, so that we can rule out practice on the test as a reason for post-training improvements. During Humphrey perimetry, the eye tracker will be engaged at all times. Tests will be repeated if the patient fails to generate acceptable test reliability (in terms of rate of fixation breaks, false positives and false negatives). If repeated perimetry tests fail to yield acceptable reliability measures (as per device specifications), this will constitute grounds for excluding the subject from the study. Our research to date shows that accurate fixation is critical both to generate reliable perimetry results (our primary outcome measure) and to elicit training-induced improvements in the blind field. All excluded subjects will be replaced with a new enrollment.

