- requires inpatient hospitalization or prolongation of existing hospitalization;
- is a congenital anomaly/birth defect; or
- requires medical or surgical intervention to prevent permanent impairment or damage.

At each subject visit the site study staff will assess adverse events by recording all voluntary complaints of the subject and by assessment of clinical and laboratory features. At each study visit, the subject should be questioned directly regarding the occurrence of any adverse experience since his/her last visit.

All adverse events, whether observed by the Investigator, elicited from or volunteered by the subject, should be documented. Each adverse event will include a brief description of the experience, the date of onset, the date of resolution, the duration and type of experience, the

severity, the relationship to investigational product, contributing factors, and any action taken with respect to the study device. All adverse events occurring between the time of consenting and subject completion or withdrawal from the study will be recorded. Follow up will continue until the adverse event is resolved, including those unresolved at the time of subject concluding study participation.

Data analysis and data monitoring: HVF test results will be analyzed using a custom program in Matlab. Changes in HVF over time will be mapped across the visual field and the area of the visual field that increases or decreases in sensitivity by >6dB will be quantified. Subject age, lesion age, visual deficit size, and type of precipitating neurologic event will be analyzed using linear regression and ANOVA to determine if any of these factors are correlated with change; when appropriate, post-hoc analyses will be conducted using Tukey's HSD and a family-wise Type I error rate of 0.05.

Data storage and confidentiality

- a. Data will be stored on a secure, encrypted server hosted on the URMC private network. Only study personnel directly involved in raw data processing and analysis will have access to data files containing protected health information.
- b. A separate key will be created linking the subject identifiers with a unique study ID number to avoid any direct identifiers stored with the collected data.
- c. Data collected will be used for future research studies.

Risks/benefit assessment

- a. Risk Category: Minimal risk

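### The plan states no model comparing the two training cohorts on the primary perimetry outcome, and so no baseline adjustment of that comparison, although a baseline field is held for every subject

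*Combined protocol and SAP*

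**What the plan says.** All references are to the combined protocol and SAP.

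- **Outcome.** Under Screening Visit, Visual field testing, the plan stresses fixation as a condition for "reliable perimetry results (our primary outcome measure"). This is the only place where an outcome is called primary.
- **Baseline.** The same paragraph says: "Examinations need to be done twice at baseline, with the second test used for future analysis".
- **Outcome measure.** Data analysis and data monitoring, the only analysis text, says: "Changes in HVF over time will be mapped across the visual field and the area of the visual field that increases or decreases in sensitivity", counting only changes above 6 dB, is what will be quantified.
- **Use of deficit size.** The next sentence says that age, lesion age, deficit size and type of neurologic event "will be analyzed using linear regression and ANOVA to determine if any of these factors are correlated with change". Training cohort is not in the list, and neither is the baseline Humphrey value. The text does not say whether the four factors are fitted one at a time or together.
- **Range of deficits.** Inclusion criterion 8 requires a deficit of "a minimum of two testing locations high and two testing locations wide". Criterion 6 admits incomplete and complete hemianopia.
- **Size and allocation.** Number of subjects: "20 subjects will be recruited at each of three study sites, leading to a total of 60 subjects", "with 30 subjects receiving one form of visual discrimination training therapy, while the other 30 will receive another form of visual discrimination training". The Randomization paragraph mentions no stratification by deficit size.

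**The concern.** The outcome is an absolute area of field. A subject who enters with four impaired locations has far less area to regain than one with complete hemianopia, so part of the between-subject spread in area gained may simply reflect deficit size at entry. If the cohorts are compared without deficit size in the model, that spread stays in the residual. With 30 per cohort and no stratification, a chance imbalance in deficit size would also move the observed difference.

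The plan holds the data needed to deal with both, but does not say that it will use them this way. Because the cohort comparison itself is unwritten, the choice between an adjusted and an unadjusted result also stays open until the data are in. That matters for results that are to go to the Food and Drug Administration.

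**Working it through.** **The plan's own figure.** 3 sites x 20 = 60, and 2 cohorts x 30 = 60, so the sample size is internally consistent. It cannot be reproduced as a power calculation: no effect size, SD, power, dropout or correlation is given. What follows is therefore a sensitivity range.

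**Inputs.** n = 30 per cohort (Number of subjects). Two-sided alpha of 0.05 is assumed, because the plan states 0.05 only as a family-wise rate for post-hoc tests. The correlation r between baseline deficit size and area changed is also assumed.

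**Benchmark.** By the normal approximation, the difference detectable with 80% power without adjustment is (1.960 + 0.842) x √(2/30) = 2.802 x 0.258 = 0.723 SD.

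**Area outcome, adjusted for deficit size.** The variance is multiplied by 1 − r². Power at the same true difference is Φ(2.802/√(1 − r²) − 1.960). Effective N is 60/(1 − r²). The last column also multiplies the variance by 1 + 1/56 = 1.018, the approximate price of estimating one covariate.

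| r | 1 − r² | SE reduction | Effective N | Power | Power after covariate cost |
|---|---|---|---|---|---|
| 0 | 1.00 | 0% | 60.0 | 80.0% | 79.3% |
| 0.1 | 0.99 | 0.5% | 60.6 | 80.4% | 79.7% |
| 0.2 | 0.96 | 2.0% | 62.5 | 81.6% | 80.9% |
| 0.3 | 0.91 | 4.6% | 65.9 | 83.6% | 82.9% |
| 0.5 | 0.75 | 13.4% | 80.0 | 89.9% | 89.4% |

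**Which r is plausible?** The documents do not say, so simulated scenarios are used. All of them are assumptions.

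- Regain proportional to deficit size, deficits uniform on 4 to 26 locations, mean regain 10–20%, between-subject CV of regain 0.3–1.0: r = 0.32–0.59, and power rises from 80% to 84–93%.
- The same model with CV 1.5: r = 0.24–0.25.
- The proportional model with deficits of 12 to 26 locations, CV 0.6–1.0: r = 0.18–0.29.
- Regain scaling with the square root of deficit size, as if it occurred along the border, CV 0.6–1.0: r = 0.20–0.25.

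The last three put r at roughly 0.2–0.3, which gives about 82–84% before the covariate cost.

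**Chance imbalance.** The standard error of the cohort difference in mean deficit size is √(2/30) = 0.258 SD, so 1 trial in 20 would show an imbalance beyond 1.96 x 0.258 = 0.506 SD. At r = 0.3 an imbalance of that size shifts the unadjusted difference by 0.3 x 0.506 = 0.15 SD, against a detectable difference of 0.723 SD.

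**Continuous summary, if one is also compared.** Replacing a change score by ANCOVA multiplies the variance by (1 + ρ)/2, where ρ is the correlation between baseline and week 29 (equal variances assumed). At ρ = 0.5 the factor is 0.75 and power goes from 80% to 90%; at 0.7 it is 0.85 and 86%; at 0.9 it is 0.95 and 82%. This formula does not apply to the area outcome, which has no baseline value of its own.

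**The case against.** A reader might infer that the plan commits to an unadjusted comparison of change and never uses deficit size. The text supports neither. It states no cohort comparison of any kind, and it does enter deficit size in a regression or ANOVA for change. If the four factors share one model, the tests of age, lesion age and event type are already adjusted for deficit size. The accurate statement is narrower: deficit size is examined as a correlate of change and is not specified as a covariate in a treatment comparison.

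A reader might also infer a sizeable, known loss of power. The larger gains come from assuming that regain is proportional to deficit size, and nothing in the plan says so. Under the Baseline Visit, training starts at a location where discrimination falls to chance on passing from the intact into the blind field. Gain may therefore follow the trained location or the border more than total deficit. The area measure also counts losses, and changes anywhere in the field. These objections stand, and they are why the range has to reach down to no gain.

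Finally, it can be said that the missing comparison model is the larger gap and that covariates are one clause of filling it. That is right as to order. But adding a t-test on area changed would fill the larger gap and still leave the baseline information unused, so the covariate needs to be named.

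**Conclusion.** The point holds in this form: the plan has no stated model for comparing the cohorts on the primary perimetry outcome and, with it, no pre-specified baseline adjustment, although the baseline field is collected in everyone and entry deficits vary widely.

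It is a matter of efficiency and pre-specification. It would be wrong to conclude that an unadjusted comparison is biased or invalid; randomisation protects it. The benefit is favourable in direction whenever deficit size is materially related to area changed, small to moderate in size, and not determinable from the documents. It runs from no gain (a loss of under one point of power after the covariate cost) at r = 0, through about 2 points at r = 0.2 and 4 at r = 0.3, to 10 at r = 0.5, starting from 80%. These figures assume 30 analysed per cohort, two-sided 0.05 and a roughly linear relation with deficit size.

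**What to change.** In Data analysis and data monitoring, before unmasking, state that:

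1. The training cohorts are compared on area changed by more than 6 dB with a linear model whose terms are cohort and baseline deficit size. Deficit size is the number of 24-2 locations below 15 dB, the threshold already used in inclusion criterion 8, on the second baseline field.
2. If a continuous Humphrey summary is also compared, its week-29 value is modelled on cohort and its own baseline value, in place of raw change.
3. Age, lesion age and event type are examined in a model that also contains baseline deficit size.

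The cost is a few sentences, one degree of freedom (about 1.8% in variance if the covariate proves useless) and an approximate linearity assumption that can be checked on the same data. No new visits, tests or staff are needed.

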Title: Visual Restoration for Hemianopia

RSRB No.: RSRB00069879

Sponsor-Investigator: [name]. M.B.A.

Principal Investigator (Study Site 1): [name]. M.B.A.
Professor and Chair, Flaum Eye Institute
University of Rochester
[name]
Rochester, NY, 14642
USA

Daytime [contact]

Sub-Investigator 1 (Study Site 2): [name].
Robert Z. & Nancy J. Greene Professor of Ophthalmology
Bascom Palmer Eye Institute
University of Miami Health Services
[name]
Miami, Florida 33136
Daytime [contact]

Sub-investigator 2 (Study Site 3): [name]
Scheie Eye Institute
Department of Ophthalmology
University of Pennsylvania
Philadelphia, PA 19104
Daytime [contact]

Purpose: This project will collect data to quantify the effect of visual training on visual defects resulting from damage to the primary visual cortex. Subjects will be recruited, undergo baseline visual testing, undergo visual training designed to reduce their visual deficit, and perform post-training visual tests. This research is designed to determine if different visual training treatments are capable of reducing visual defects in a large population of adult subjects with cortical blindness in a double blind clinical trial.

Background and Motivation for the study: When brain damage is incurred in adulthood, through stroke, trauma, or other neurodegenerative conditions, functional deficits result depending on the brain region that was affected. As roughly half of the human cerebral cortex is devoted to visual processing, many people who suffer brain damage experience consequent impairments in vision. When damage affects the primary visual cortex (V1), the visual deficits are severe and are described as cortical blindness (CB), or hemianopia/quadrantanopia, depending on the size of the defect. CB dramatically impacts the lives of those affected, decreasing quality of life (Gall et al., 2008; Gall et al., 2009; Gall et al., 2010). CB subjects often lose the ability to drive (de Jong and Warmink, 2003; Papageorgiou et al., 2007), reducing their independence, while others who continue to drive pose a potential danger to themselves and others (Bowers et al., 2009, 2010; Bowers et al., 2014). Those suffering from CB also have other types of impaired daily functioning (Ramrattan et al., 2001), and reduced independence (Jongbloed, 1986).

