- b. Potential Risks: There are no known risks of the visual tests and examinations used in this study. There are also no known risks of the visual training to be used. Subjects may become tired during the course of testing and/or training. There is a risk that subject confidentiality will be breached. In addition, as the visual training used in this study is experimental, there may be unknown risks.
- c. Protection against risks: If a subject becomes tired during the course of testing or training, they will be allowed to rest until they feel ready to continue. Subject confidentiality will be protected as well as possible through the use of de-identified ID numbers and secure data transmission.
- d. Benefits: We cannot promise any benefits of taking part in this research. However, possible benefits include an expansion of the subjects' visual fields through the reduction of the cortically blind deficit, and improved visual functioning in portions of the visual field.
- e. Alternatives to participation: Alternatives may include visual training programs or other research studies.

Subject identification, recruitment, and consent/assent

1. Method of subject identification and recruitment: Subjects will be recruited for this study from the clinical practices of the three sites, as well as from waiting lists of subjects who have previously contacted the study sites. If additional subjects are required, we will widen the search to include the clinical practices in the immediate areas near each study site. Examples of the expanded recruitment pool include online hospital recruitment databases such as Iconnect and other forms of digital recruitment. Candidate subjects will then be randomly selected for screening by our inclusion/exclusion criteria. If a subject fails the screening process they will be replaced with a new subject randomly selected from the waiting pool.

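### The >6 dB change area is taken across the whole visual field and not reported separately for the baseline deficit, so it is a non-specific measure of deficit reduction.

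*Combined protocol and SAP*

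**What the plan says.** All references are to the combined protocol and SAP.

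- **Aim.** Under Purpose, subjects will "undergo visual training designed to reduce their visual deficit". The Benefits item of the Risks/benefit assessment describes a possible expansion of the visual field "through the reduction of the cortically blind deficit", and also better visual function in parts of the field.
- **Outcome.** Visual field testing, under the Screening Visit, calls perimetry results the primary outcome measure but names no summary of them. Two Humphrey fields are taken at baseline, and the second is the one used for analysis.
- **Measure of change.** Data analysis and data monitoring states that "the area of the visual field that increases or decreases in sensitivity by >6dB will be quantified". The mapping behind this is described without any limit to a region of the field. This is the only perimetric change measure described. Deficit size appears in that section only as a factor to be related to change.
- **Definition of impairment.** Inclusion criterion 8 sets the smallest eligible deficit at two by two test locations. For that purpose, "impaired locations are any that measure a threshold of less than 15 dB". The 15 dB line is not used again. Criterion 6 admits "a stable homonymous incomplete (e.g., quadrantanopia or relative defect) or complete hemianopia".

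**The concern.** The question is whether the deficit shrinks, but the only described measure covers the whole tested field. A gain of more than 6 dB at a location that was never impaired enters the area on the same footing as one inside the blind field. The smaller the deficit, the more of the field lies outside it, and the more of the reported area can come from retest variation there.

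This matters more because both cohorts train and the analysis section states no comparison of this area between them. No untrained group shows how much change arises without training. A reading within cohorts (area gained, therefore training works) would take in retest variation and any remaining practice effect in the seeing field. The results are meant for regulatory submission, so the region should be fixed before the data are seen.

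**Working it through.** The plan gives no figure for this measure, so there is nothing to reproduce. Three checks were made.

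**1. How the 6 dB rule relates to the 15 dB line (whole-dB steps, documents only).** A counted gain is at least 7 dB. Leaving the deficit means going from below 15 dB to 15 dB or more.

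- Baseline 0 to 7 dB: a counted gain can leave the location impaired (0 + 7 = 7; 7 + 7 = 14).
- Baseline 8 dB: the two rules agree for every gain (8 + 7 = 15).
- Baseline 9 to 14 dB: a gain of 6 dB or less can reach 15 dB and not be counted (9 + 6 = 15; 14 + 1 = 15).
- Baseline 15 dB or more: a gain above 6 dB is counted although the location was never in the deficit.

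So the area gained is not the same quantity as shrinkage of the region below 15 dB.

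**2. Noise-only gains outside the deficit.**

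- From the documents: the 6 dB threshold, and a minimum deficit of k = 2 × 2 = 4 locations.
- Assumed: M = 52 usable locations; retest difference D normal with mean 0 and SD 2 to 5 dB.
- Formula: expected false gains outside the deficit = (M − k) × P(D > 6), where P(D > 6) = 1 − Φ(6/SD).

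| SD of D (dB) | P(D > 6) | 48 outside (k = 4) | 26 outside (k = 26) | 4 inside (k = 4) |
|---|---|---|---|---|
| 2 | 0.0013 | 0.06 | 0.04 | 0.01 |
| 3 | 0.0228 | 1.09 | 0.59 | 0.09 |
| 4 | 0.0668 | 3.21 | 1.74 | 0.27 |
| 5 | 0.1151 | 5.52 | 2.99 | 0.46 |

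At most 4 true gains are possible inside the smallest deficit. With M between 40 and 60 and SD 4 dB, the k = 4 figure outside runs from 2.41 to 3.74. If errors are independent with equal variance, the 48 outside locations carry 48/4 = 12 times the noise variance of the 4 inside.

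**3. Whether restricting to locations below 15 dB creates its own bias.** This was simulated with no true change, true sensitivity uniform on 0 to 30 dB, readings floored at 0, and change computed from the second baseline field (all assumed). A per-test SD of s gives a difference SD of s × √2 away from the floor.

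| Per-test SD (difference SD), dB | Mask on second field: gained / lost | Mask on first field: gained / lost |
|---|---|---|
| 2.1 (3) | 2.4% / 1.4% | 1.9% / 1.9% |
| 2.8 (4) | 7.4% / 3.9% | 5.7% / 5.7% |
| 5 (7.1) | 23.6% / 10.4% | 17.0% / 17.0% |

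Selecting locations on the same field that serves as baseline makes gains exceed losses when nothing has changed. Selecting on the other baseline field removes that imbalance. The last row is noisier than any case in check 2 and only shows the direction.

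**The case against.** A reader might infer that the measure does not capture deficit reduction at all. The documents do not support that: every gain above 6 dB at an impaired location is counted. Change is also mapped by location, so a deficit-only summary could be derived from the same data. That stands, but the plan does not commit to one, and choosing the region afterwards would be post hoc.

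A reader might also infer from check 1 that the plan contradicts its own definition of recovery. It does not. The 15 dB line is an eligibility rule and nowhere the boundary of recovery. Relative defects are eligible, and the Benefits item includes better function in parts of the field, so a rise from 0 to 14 dB fits the aims. A decibel-change threshold is a legitimate choice.

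Third, subjects are randomised and masked, so seeing-field noise would mainly add variance to a contrast between cohorts rather than bias it. That is correct, but no such contrast is stated for this area, and the added variance is itself a cost. Losses above 6 dB are quantified too, which gives some check on symmetric noise, and the second baseline test is meant to deal with practice. Neither shows whether the change lies in the deficit.

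Finally, the size rests on an assumed grid and SD, takes the smallest eligible deficit as its worst case, and counts locations where the plan measures area. All of this stands. At an SD of 2 dB the effect is negligible.

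**Conclusion.** The point holds as one of specificity. As written, the change area covers the whole field, and the plan neither restricts it to the baseline deficit nor reports that part separately. It is a non-specific measure of deficit reduction, not an unrelated one, and the documents do not formally name it as the primary endpoint.

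On the stated assumptions, the size runs from negligible at a retest-difference SD of 2 dB to about 1 to 5.5 falsely gained locations at 3 to 5 dB for a 4-location deficit, and about 0.6 to 3.0 with 26 seeing locations. That the region is unspecified follows from the text alone and needs none of these assumptions. This is a cheap improvement, not a fault that invalidates the trial.

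**What to change.** In Data analysis and data monitoring:

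1. Keep the 6 dB threshold. Report the area gained and the area lost separately within the baseline deficit, defined as locations below 15 dB (inclusion criterion 8).
2. Report the same two areas for the rest of the field as a separate retest and practice reference.
3. Define the deficit region on the first reliable field of the baseline pair, or of the repeat pair if fields are redone at Visit BL. Compute change from the second field, which the protocol already makes the analysis baseline.
4. As a companion and not a replacement, report the net change in area below 15 dB from the second baseline field to post-training. Do not also require a gain above 6 dB, because that would again miss moves from 9–14 dB to 15 dB.

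**Cost.** A masking step in the existing Matlab program and a paragraph of text; no new data. There are two downsides. Gains in relative defects at or above 15 dB move to the separate summary. A less-practised first field may also bring some seeing locations into the mask.

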Randomization: Eligible subjects will receive their randomization assignment. All subjects will be double masked. Treatment locations and training cohort will be pre-assigned for all subject ID numbers and given to each subject at the end of visit BL. The site will then call the DCBC to obtain the subject ID to be used for each randomized subject and enter this number into the training software, which includes the randomized stimulus sequence.

3 – Post training visit (28 week visit +/- 2 weeks)

Eye fixation testing and restoration protocol testing: The eye fixation testing and protocol testing will be repeated as described for visit BL.

The National Eye Institute Visual Functioning Questionnaire – 25 (VFQ-25) version 2000 and supplement will be repeated, as described for Visit BL.

4 – Post training clinic visit (29 week visit +/-2 weeks)

Eye examination: The history and eye examination will be repeated as described for Visit SC.

Visual field testing: Visual field testing will be repeated as described for Visit SC.

Assessment Schedule

Visit Number	1 (screening)	2 (2-4 weeks post screening)	3 (28 weeks +/- 2 weeks)	4 (29 weeks +/- 2 weeks)
Informed Consent	Y			
Inclusion/Exclusion Criteria	Y			
Demographics	Y			
Medical History	X			X
Concomitant Medications	X			X
Slit-lamp exam	X			X
Retinal Optical Coherence Tomography	X			X
24-2 Humphrey	X			X
24-2 Humphrey repeated	X			X
MRI/CT	Z			
Comprehensive routine dilated eye exam*	X			X
Visual Functioning Questionnaire		Y	Y	
VFQ supplement		Y	Y	
MAIA perimetry		Y	Y	
Eye fixation testing and restoration protocol		Y	Y	

X Performed by clinician

Y Performed by study personnel

Z From patient chart

*dilated fundus exam, Snellen best corrected acuity, intraocular pressure, exophthalmometry, motility, external exam

Unscheduled telephone contacts: These contacts may be initiated by the sites in response to contact from the TC indicating compliance (e.g. missed training sessions) or performance issues (e.g. fixation losses). These contacts may be initiated by the subject for any reason, including equipment failure, motivational issues, or notification of inter-current events that may affect training. The date and reason for the unscheduled telephone contact will be recorded in the source documentation.

Unscheduled visits: These visits may be initiated by the sites in response to contact from the TC indicating compliance (e.g. missed training sessions) or performance issues (e.g. fixation losses).

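### Perimetry is called the primary outcome, but the plan defines no single per-subject variable, eye rule or between-cohort comparison; its only numerical summary, area changing by more than 6 dB, leaves several candidate results open

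*Combined protocol and SAP*

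**What the plan says.** All references are to the combined protocol and SAP.

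- **Outcome.** The visual field testing paragraph under Screening Visit says accurate fixation is needed to "generate reliable perimetry results (our primary outcome measure". That paragraph concerns the 24-2 Humphrey field (HVF), so I read the primary outcome as Humphrey perimetry. MAIA perimetry is also done at baseline and after training ("The eye fixation testing and protocol testing will be repeated as described for visit BL"), but its stated purpose is fixation quality.
- **Summary.** Data analysis and data monitoring says HVF change will be mapped and that "the area of the visual field that increases or decreases in sensitivity by >6dB will be quantified". The map is descriptive. The area is the only number named.
- **Models.** The same paragraph relates age, lesion age, deficit size and type of event to change, by regression and ANOVA. Training cohort is not in that list. The one error rate given, "a family-wise Type I error rate of 0.05", is attached to post-hoc Tukey comparisons.
- **Timing.** Fields are done twice at screening, "with the second test used for future analysis". At the 29-week visit, "Visual field testing will be repeated as described for Visit SC".
- **Size.** "20 subjects will be recruited at each of three study sites, leading to a total of 60 subjects", "with 30 subjects receiving one form of visual discrimination training therapy, while the other 30 will receive another form". No power, effect size, SD of change or dropout rate is given.

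**The concern.** The background justifies this trial by the lack of randomisation and blinding in earlier studies, and says the results will go to the FDA. Randomisation and masking do not protect the result if the primary variable can be chosen after the codes are known.

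As written, an analyst could report gain, loss or net area; in the right eye, the left eye or both combined; over the whole field or the deficit. That is 3 × 3 × 2 = 18 definitions, all consistent with the text. Nor is the comparison that would answer the trial's question, one cohort against the other, specified.

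A second issue is efficiency. A cut at 6 dB ignores smaller changes at each location and the size of larger ones. With 30 per cohort, the choice of variable could matter a good deal.

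**Working it through.** **Inputs.** From the documents: 60 subjects, 30 per cohort; the 6 dB cut; the 15 dB definition of an impaired location (inclusion criterion 8). Everything else is assumed: two-sided 5%, no dropout, and the noise and effect sizes below. The plan has no power figure to reproduce.

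**1. What 30 per cohort can detect with one pre-named variable** (normal approximation, d = standardised difference).
- 80% power: d = (1.96 + 0.84) × √(2/30) = 2.80 × 0.258 = 0.72.
- 90% power: (1.96 + 1.28) × 0.258 = 0.84.
- At d = 0.5, power is Φ(0.5/0.258 − 1.96) = 49%.

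**2. Cost of leaving candidates open.** For k independent tests at 5%, the chance of at least one false positive is 1 − 0.95^k: 9.8% for k = 2, 14.3% for k = 3, 18.5% for k = 4. Correlation between candidates lowers these figures. Net area is built from gain and loss, so adding it costs less than the step from 9.8% to 14.3%. For gain and loss alone, a null simulation gave about 9 to 10%. The formula should not be applied to all 18 definitions, which overlap heavily.

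**3. Power, small uniform shift, independent locations.** Relative efficiency of the cut against the mean is E = φ(c)²/[Φ(c)(1 − Φ(c))], with c = 6/SD and SD that of change at one location. A measure with 80% power falls to Φ(2.80 × √E − 1.96). At SD 4: c = 1.5, E = 0.1295²/(0.9332 × 0.0668) = 0.269, and power is Φ(2.80 × 0.519 − 1.96) = 31%.

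| Location SD (dB) | E | Power, from 80% |
|---|---|---|
| 2 | 0.015 | 5% |
| 3 | 0.131 | 17% |
| 4 | 0.269 | 31% |
| 5 | 0.370 | 40% |
| 6 | 0.439 | 46% |

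**4. Power by simulation.** 30 per cohort, 54 locations of which 25 are in the deficit, normal noise, between-subject SD 0.5 to 2 dB, t-tests, 1,500 runs per setting. Location SD is 2 to 6 dB for the two shift scenarios and 2 to 4 dB for the focal one. Areas are counted over the whole field. Ranges run across settings.

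| Effect | Whole-field mean | Deficit mean | Gain area | Net area |
|---|---|---|---|---|
| Uniform shift, whole-field mean set near 80% | 77–82% | 54–79% | 11–73% | 16–80% |
| Shift in deficit only, deficit mean set near 80% | 26–42% | 79–82% | 7–27% | 7–35% |
| 8 dB gain at 3 locations | 12–86% | 41–100% | 29–100% | 17–100% |

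In the second row much of the loss comes from region, not from the cut: the whole-field mean itself drops to 26–42%. In the third row gain area beats the whole-field mean in 9 of 9 settings. It beats the deficit mean in 6 of 9, all at location SD 2 or 3 dB, and two of those six are ties near 100%. At SD 4 dB the deficit mean is ahead.

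**The case against.** The strongest defence is that area fits the design. Training starts at a chosen blind-field location, treatment locations are pre-assigned, and the hoped-for benefit is an expanded field and better function in portions of it. Such gains may well be focal, and then a mean dilutes them. The area is also a quantitative per-subject measure, not a split of subjects into responders and non-responders. Areas produced by test noise arise in both masked cohorts alike, so they add variance rather than bias. Pre-naming gain area or net area would cure the multiplicity just as well as a mean.

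All of this stands, and it limits the power argument. A reader might infer that the cut loses up to half the power, or that a mean dB measure would recover power at no cost. The documents support neither. They give no noise or effect size, and under plausible assumptions the cut can cost well over half, cost almost nothing, or help. So half is not a bound, and moving to a mean is a trade-off.

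It is also true that the plan nowhere says it will test gain and loss separately. The 9.8% is the price of a strategy that the text permits, not one that it announces. None of this supplies the missing variable, eye rule, region or cohort comparison.

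**Conclusion.** The concern holds as a gap in definition. The primary domain is named; the per-subject variable, direction, region, eye rule and between-cohort test are not. The cost is a false-positive rate of about 10% if gain and loss areas are each tested at 5%, assuming near-independence. It could be higher with more candidates, and is lower where they are correlated.

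On power the conclusion is conditional. If gains are small and diffuse, the 6 dB cut can lose substantial power. If they are focal, it loses little or can gain. Which applies depends on noise and effect pattern, and neither is in the documents.

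The point should be corrected before unmasking. It does not show that the area measure is wrong or that the treatment comparison is biased.

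**What to change.** Before unmasking, add a short statement to Data analysis and data monitoring that:

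1. Names one per-subject primary perimetric variable, its field region, the rule for combining eyes, and which of the two fields at each visit is used. The second-test rule is written for baseline only.
2. Compares it between the two cohorts by ANCOVA adjusted for its baseline field value, two-sided 5%.
3. Reports the >6 dB gain and loss areas as supporting results, with the maps.

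A suitable candidate is mean dB change over locations below 15 dB at baseline, averaged over both eyes. Selecting locations on the baseline field will produce some upward regression, but in both cohorts alike. If the investigators expect focal gain, pre-naming gain or net area would also settle the multiplicity.

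The cost is wording only: the schedule already has two Humphrey fields at screening and two at 29 weeks. The drawbacks of the mean are that it can dilute focal gain and does not show spatial extent. It also rests on few locations when the deficit is small: criterion 8 admits a 2 × 2 block, which is four points. Inclusion criterion 6 admits relative defects, so a 15 dB limit may leave out milder impaired locations. The statement should say that this is accepted.
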